Gaston, Porter, & Thomas 52 created an intervention designed to improve knowledge about major illness and nutrition for midlife Black women. This intervention used a support group approach to increase awareness and engagement. In another study, civic engagement was used to promote participation in lifestyle behaviors that reduce CVD risk. The adapted intervention was conducted in churches and 'change clubs' were formed. The 'change clubs' created a social network and group dynamic centered on improving lifestyle behaviors. Both studies aimed to improve general health. Culturally relevant approaches were identified but specific risk factors (i.e. stress) were not addressed.

Stress Interventions: Stress-reduction intervention studies aimed at Black women have targeted health problems such as pre-term labor, high blood pressure, and obesity. These health problems have demonstrated strong associations with stress and alarming disparities for Black women. In a study by Wesley,56 on-to-one sessions using deep breathing exercises or guided imagery were successful in decreasing perceived stress scores in pregnant Black women. Another study by Lechner and colleagues,57 used cognitive behavioral stress therapy to improve psychological adaptation in a sample of Black female breast cancer survivors. Alternatively, Cox and colleagues did not find significant success in their stress-augmented weight loss intervention program for adult Black women.55 Engagement was a key mediator related to lack of adherence to the intervention55 and is often proposed as a rationale for gender and cultural tailoring. These studies demonstrate a willingness of Black women to use a variety of stress-reduction strategies and highlights the importance of culture and inclusion when delivering interventions. No intervention studies were found that focus on the life stressors relevant to midlife Black women and the mechanisms through which these stressors serve as barriers to health lifestyle behavior.

3.3.4. Technology Use During COVID-19 Pandemic.

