Program evaluation will be ongoing. Data collection telephone interviews will occur at three time points: baseline (pre-intervention), 8 weeks (completion of the study), and 12 weeks (4 weeks post intervention) for both the B-SWELL and WE groups. Outcome measures will include LS7 scores, number of unhealthy days, depressive symptoms, and perceived general health. Ratings will be obtained from community collaborators to evaluate recruitment, retention, and treatment fidelity for both groups. Qualitative feedback and satisfaction ratings for the B-SWELL groups, WE groups, and technology will be obtained from participants at completion.

Recruitment and Eligibility: Aim 2: The sample of participants for Aim 2 will consist of 50 Black or African-American women randomized to a B-SWELL group (n=25) or to a WE attention control group (n=25). Inclusion criteria include being Black or African-American, between the ages of 40 and 64, fluent in the English language, ability to hear and speak well enough to engage in everyday conversation, access to a telephone, access to WIFI and willingness to participate. Exclusion criteria include recent immigration to the U.S., prisoner or on house arrest, pregnant, terminal illness (i.e., late stage cancer, end-of-life condition, renal failure requiring dialysis), history of Alzheimer's, dementia, or severe mental illness (i.e., suicidal tendencies, schizophrenia, or severe untreated depression), or any other major health conditions or disabilities (i.e. visual impairment, blindness, deafness) prohibiting safe or full participation in the program. Recruitment will involve use of fliers, referral, snowballing, and purposeful sampling in targeted communities. Fliers may be posted in businesses, on list serves, or group websites to increase distribution. The 8-week trial will take place virtually using a Zoom account established through the UC CON for the PI. Dates and times of the online virtual sessions will be established based on availability of the participants following randomization.

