Interventions and Treatment Fidelity Methods: The B-SWELL intervention will follow procedures such as those proposed in Figure 1 and will be refined prior to trial based on feedback from the community collaborators and expert ratings (Aim1). Participants will be randomized to either the B-SWELL or WE groups. Both groups will be introduced to the LS7 materials. The B-SWELL will receive additional instruction about stress. B-SWELL and WE group sessions will occur on different dates and times and, participants will be asked not to share experiences with women outside of their assigned group. Participants will also be asked to secure private location when attending the virtual sessions to ensure privacy and confidentiality. Treatment fidelity of both groups will be monitored using Borrelli's Treatment Fidelity Checklist (Design, Training, Delivery, Receipt, Enactment). Facilitators of the intervention and control groups will be trained prior to the start of the trials.. Zoom meetings will be audio taped for quality assurance.

Data Collection Procedures: Aim 2. Data collection will occur at baseline, 8 weeks, and 12 weeks. Baseline data will be collected from B-SWELL and WE participants using telephone interviews conducted by trained, blinded research assistants. Data collection at 8 and 12 weeks may be collected via phone interview or through a REDCap link on the B-SWELL study tablets provided to B-SWELL and WE participant. Completion of the surveys (interview or via REDCap link) is expected to last 30-45 minutes for each timepoint. Instruments are listed in Table 5. 3.4.d.

Randomization Procedures: Following baseline data collection, participants will be randomized to either the B-SWELL or WE group using 1:1 block randomization to promote equal group sizes. The randomization allocation sequence will be blinded to data collectors to avoid bias during follow-up data collection telephone interviews. Following randomization, the PI or research assistant will notify the participant of their group assignment and upcoming group meetings. Treatment fidelity will be monitored using the Borrelli's Treatment Fidelity Checklist (Design, Training, Delivery, Receipt, Enactment).

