17.0 Data Management* and Confidentiality

17.1 Describe the data analysis plan, including any statistical procedures or power analysis.

In Aim 1 and Aim 2a, numerical measures will be summarized using descriptive statistics (i.e., means, standard deviations, and frequencies) regarding expert ratings of degrees of accuracy, relevance and feasibility of new components of the B-SWELL program (Aim 1), and recruitment, retention, treatment fidelity ratings, and satisfaction ratings (Aim 2a). For Aims 2b and 2c, numerical dependent variables (stress, self-efficacy, LS7 scores, unhealthy days, perceived general health, depressive symptoms) will be inspected of empirical distributions to ensure they meet conditions for parametric statistical models. Variable transformation will be used otherwise. All statistical tests will be performed using SPSS Version 25. Parameter estimates with P-values less than .05 will be considered statistically significant. Assumptions related to each statistical test used will be checked using residual plots, qq-plots, and tests for homogeneity of variance/ covariance. In Aim 2b, continuous mediators (stress, self-efficacy) will be compared between groups (B-SWELL vs WE) using t-tests at each visit (baseline, 8 weeks, 12 weeks).

In Aim 2c, using mixed effect models, primary (i.e., LS7 summary scores) and secondary outcome measures (i.e., unhealthy days, perceived general health, depressive symptoms) will be assessed for their associations with time (baseline, 8 weeks, 12 weeks), group (B-SWELL vs. WE), and interaction. In particular, each of the outcome measures will be treated as the dependent variable, and the time effect, group effect, and the interaction will be treated as independent variables or fixed effects of interest in the mixed effect model. Random effects will be used to account for within person correlation due to repeated measurements. Other covariates, such as demographics and attendance rate, will be controlled for by including them in the model and checking for their interaction with the intervention. Post hoc analysis of group means will be compared cross-sectionally, as well as longitudinally between time points (such as week 8 or 12 vs. baseline). Considering the limited sample size for this pilot-type of study, statistical tests will not be adjusted for multiple comparisons in post hoc analyses. Significant findings will be considered preliminary in nature and inspire future research.

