Power. Statistical power is analyzed based upon assumptions that we have N=50 total or N=25/group complete all four data collection time points with complete observations. Should there be any concern of dropout from the study, we will over sample participants at baseline to offset the predicted dropout rate and ensure the proposed sample size in the final visit. The statistical tests are two sided with a targeted significance level of 0.05. In Aim2b and Aim2c post hoc analyses when we compare means using a two group t-test with equal variances assumption, we will reach 85% power to detect an effect size (i.e. difference of means/standard deviation of the difference) of 0.87.73 In Aim2c when we compare means using a paired t-test between visits in a group, we will reach the 85% power to detect an effect size of 0.63.73 If possible, and plausible, missing data could be included into analysis after multiple imputation, thus increasing the sample size and statistical power to detect differences. The main emphasis will be on exploring data trends to inform future work, rather than

significance, since this is a feasibility study. Significance will be emphasized when testing efficacy of the B-SWELL intervention compared to the WE attention control group in a future, well-powered RCT.

17.2 Describe the steps that will be taken to secure the data during storage, use, and transmission.

All study data and tracking will be entered into an electronic data system, REDCap (www.REDCap.org), a secure research electronic data management system with validated data entry, audit trails for tracking data manipulation, and export procedures. It is HIPAA complaint satisfying all local, state, and federal regulation for the capture and storage of private health information for research purposes. The PI is familiar with RedCap through prior research projects. The PI is committed to compliance with HIPAA, data safety procedures, NIH recommendations, and CITI trainings. All research personnel will be trained in the use of secure data and RedCap prior to their participation in the study and any communication with participants.

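### The Aim 2c mixed models adjust for attendance rate, which arises after randomisation; if attendance differs by arm and tracks the outcome, the group effect is no longer the effect of assignment

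*Combined protocol and SAP*

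**What the plan says.** Aim 2c (section 2.1) is a comparison of the randomised groups at 8 and 12 weeks. Section 17.1 plans a mixed model for each outcome (LS7 score, unhealthy days, general health, depressive symptoms), in which "the time effect, group effect, and the interaction will be treated as independent variables or fixed effects of interest in the mixed effect model". On covariates it then says that "covariates, such as demographics and attendance rate, will be controlled for by including them in the model and checking for their interaction with the intervention". No Aim 2c mixed model without attendance is described, and the attendance-adjusted model is not labelled secondary or dose-response.

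Post hoc comparisons of group means, both at a visit and between visits, follow in the same paragraph without a stated method. The power paragraph of section 17.1 refers to a plain test: "In Aim2b and Aim2c post hoc analyses when we compare means using a two group t-test with equal variances assumption".

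On timing, section 6.2.2 places randomisation after baseline data collection and adds: "Dates and times of the online virtual sessions will be established based on availability of the participants following randomization". It also says that "B-SWELL and WE group sessions will occur on different dates and times", and that B-SWELL receives extra instruction on stress.

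**The concern.** Adjusting for a baseline variable leaves the randomised comparison intact. Adjusting for something that assignment can change does not. Attendance exists only once women know their group and their schedule, and the two programmes differ in content and timing. A culturally tailored programme might well be attended better than general wellness education. Section 3.3.3 reports of one earlier stress-augmented weight-loss programme that "Engagement was a key mediator related to lack of adherence", and notes that engagement is a common reason for tailoring.

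If attendance differs by arm and is related to the outcome, holding it constant compares women of unlike motivation, or removes part of what the programme achieved by bringing women to sessions. The group effect is one of three stated effects of interest, and section 6.1 says the findings will support a larger trial. A group estimate that looks null when assignment helped, or non-null when it did not, would mislead that next step.

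**Working it through.** **1. The plan's own figures.** Section 17.1 gives 25 per group, two-sided 0.05, and 85% power at effect sizes of 0.87 (two-group t-test) and 0.63 (paired).
- Two-group: df 48, noncentrality 0.87 × √(25/2) = 3.08; exact power 85.4%.
- Paired: df 24, noncentrality 0.63 × √25 = 3.15; exact power 85.6%.

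Both reproduce. They concern unadjusted tests and do not bear on the attendance question.

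**2. Formula.** With complete, balanced data and attendance entered as a main effect:

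adjusted group contrast = effect of assignment − b × D,

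where b is the within-arm slope of outcome on attendance (averaged over visits) and D is mean attendance in B-SWELL minus WE. With both variables in SD units, b equals the within-arm correlation r. The shift is zero if either b or D is zero. If WE attends better, its sign reverses.

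**3. Assumed inputs.** The documents give no attendance rate, arm gap or correlation. Assumed: r = 0.21, 0.35 or 0.49; D = 0, 0.3, 0.5 or 0.8 SD; outcome SD 1; within-person correlation 0.6; three visits (section 6.2.2); 25 per arm; complete data. The model has time, group, group-by-time, attendance and a random intercept, in line with "Random effects will be used to account for within person correlation due to repeated measurements". There were 6,000 simulated trials per cell.

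**4. No true effect, r = 0.35.**

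| Arm gap D (SD) | 0 | 0.3 | 0.5 | 0.8 |
|---|---|---|---|---|
| Formula, −0.35 × D | 0 | -0.105 | -0.175 | -0.280 |
| Simulated group main effect | 0.002 | -0.108 | -0.178 | -0.280 |
| False positives, group main effect | 5.2% | 7.7% | 12.3% | 20.8% |
| Simulated model-based week-8 contrast | 0.002 | -0.110 | -0.178 | -0.279 |
| False positives, week-8 contrast | 5.4% | 6.8% | 9.8% | 16.6% |

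The Monte Carlo standard error of the estimates is at most 0.005. Without attendance in the model the group main effect stays within 0.003 of zero, with 4.5–5.3% rejections. Group-by-time stays within 0.004 of zero, with 4.8–5.4% rejections.

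Over the same gaps the bias is 0.00, -0.06, -0.11 and -0.17 at r = 0.21, and 0.00, -0.15, -0.24 and -0.39 at r = 0.49.

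**5. True effect of 0.50 SD at 8 and 12 weeks, r = 0.35.** Over the four gaps the model-based week-8 contrast reads 0.50, 0.40, 0.33 and 0.23; group-by-time reads 0.50–0.51 throughout. The visit-averaged group effect is truly (0 + 0.50 + 0.50)/3 = 0.33. At a gap of 0.8 it reads 0.06, and its rejection rate falls from 32% (no gap) to 5%.

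**6. Does the mechanism matter?** A large simulation (200,000 per arm, true effect 0.50) compared two cases: attendance only marks a stable trait, or attendance itself changes the outcome after baseline. At gaps of 0, 0.5 and 0.8 SD the adjusted 8-week contrast was 0.50, 0.40 and 0.33 in the first case and 0.50, 0.40 and 0.34 in the second. Both models left group-by-time at 0.50, because attendance is one value per woman and cancels from her change since baseline.

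**7. The interaction check.** If an attendance-by-group term is kept uncentred, the group coefficient describes a woman who attended nothing. Assuming WE attendance of about 70%, SD 18 points and a gap of 0.5 SD, its standard error is 1.09. It is 0.29 with attendance as a main effect only, and 0.28 without attendance.

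**The case against.** The best defence is that the natural treatment comparison is group-by-time, which attendance does not disturb. Because baseline is a response visit, the group term is not the 8- or 12-week effect even without attendance: it is either the baseline difference or an average over all three visits. The power paragraph also suggests that the cross-sectional comparisons are plain t-tests, which would make the week-8 figures above an analysis nobody planned.

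Much of this is right, and the week-8 contrast matters only if those comparisons are taken from the model. But section 17.1 does not single out group-by-time. It lists group alongside it as an effect of interest and counts any estimate with P below .05 as significant. The group term therefore remains exposed.

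Other points have some force:
- Section 19.2 plans duplicate sessions where possible, availability-based times and reminders, with no distinction by arm. This makes a gap due to scheduling less likely but leaves differences due to content.
- The engagement remark in section 3.3.3 concerns one cited programme. It makes a gap plausible and does not show one.
- Section 17.1 speaks of checking interactions, not of keeping them uncentred, so step 7 is a warning about coding.
- At a gap of 0.3 SD the bias of 0.11 is less than half the 0.28 standard error.
- The study calls its findings preliminary and puts data trends ahead of significance. That lowers the stakes, but a biased estimate misstates a trend as well.

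**Conclusion.** The point holds. As written, the plan conditions its group effect on a variable that assignment can influence. The bias is −b × D: nil if attendance does not differ by arm or is unrelated to the outcome (and no attendance-by-group term is kept). Under the assumed non-zero gaps and correlations it runs from 0.06 to 0.39 SD, and false positives for the group effect reach 21% at r = 0.35 and a gap of 0.8 SD. Neither size nor direction can be known in advance. The group-by-time terms are safe with complete data and no attendance-by-time term, and so are unadjusted t-tests. In an exploratory pilot this is an error of analysis text that should be fixed; it is not a fatal flaw.

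**What to change.** In section 17.1:
- Remove attendance rate from the Aim 2c covariates and from the interaction checks. Adjust only for named variables measured before randomisation, chosen from the demographic items in the survey table of section 6.3. Baseline outcome stays as a response visit.
- State that group-by-time at 8 and at 12 weeks against baseline is the treatment comparison.
- Say whether the cross-sectional post hoc comparisons come from the model or are unadjusted t-tests.
- Report attendance by arm under Aim 2a, for example with the Receipt domain of the fidelity checklist. Label any model relating attendance to outcome as exploratory and non-randomised.

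The cost is a few sentences. Data collection, enrolment and the basic model structure do not change, and the dose-response question can still be explored under its proper label.

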Tablets will be programmed with content and links relevant to the B-SWELL study and appropriate restrictions. Programming will be conducted by the B-SWELL research team under guidance of UC CATER staff. All study materials, including tablets, will be handled in accordance with UC COVID-19 protocols (i.e. gloves and masks).

• All drugs and devices used in the research and the purpose of their use, and their regulatory approval status.

N/A

• The source records that will be used to collect data about subjects. (Attach all surveys, scripts, and data collection forms.)

All study data and tracking will be entered into an electronic data system, REDCap (www.REDCap.org), a secure research electronic data management system with validated data entry, audit trails for tracking data manipulation, and export procedures. It is HIPAA complaint satisfying all local, state, and federal regulation for the capture and storage of private health information for research purposes.

Zoom accounts have been purchased by the UC CON. Zoom accounts will be supported by the UC CON CATER technology experts. Zoom links have been determined to be secure and appropriate for research by the UC depart of research. Members of the B-SWELL research team will be trained in the use and management of online Zoom group sessions, privacy, and technical issues.

The surveys used to collect data are included in the chart below and attached.

Construct	Survey Tool	Time	Baseline	8wks	12wks
Moderators	Demographic data: income, marital status, children, education, health problems, and community of residence (among others).	5	Х		
Mediator	Cohen's Perceived Stress Scale (PSS-10): measures perception of general stress. Items are rated on a scale of $0-4$ (Max score =40). ^{66,67} Higher stress levels correspond with higher scores.	5	X	Х	X
Mediator	General Self-Efficacy Scale (GSE): 10-item psychometric scale that assesses optimistic self-beliefs to cope with life demands ^{.68}	5	Х	Х	Х
Primary Outcome	AHA Life's Simple 7 (LS7): developed to promote cardiovascular health in accordance with the organization's 2020 Impact Goals. ⁶⁹ Risk behaviors scored 0 to 2. Higher scores indicate trend towards optimal health behaviors and lower risk for CVD.	5	X	X	X
Secondary Outcome	Number of Unhealthy Days (UD): Number of days in past month participant felt physical/mental health was not good. ⁷⁰	2	Х	Х	Х

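### The Aim 2c models adjust for attendance, which arises after randomisation, and check an open-ended covariate list for interaction with the intervention in 50 women

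*Combined protocol and SAP*

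**What the plan says.** Section 17.1 plans a mixed model for each of four Aim 2c outcomes: LS7 summary score, unhealthy days, perceived general health and depressive symptoms. The fixed effects of interest are time (baseline, 8 and 12 weeks), group, and their interaction. The section then adds that further covariates, with demographics and attendance rate as its examples, "will be controlled for by including them in the model and checking for their interaction with the intervention".

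The survey table in section 6.3 lists, under Moderators: "Demographic data: income, marital status, children, education, health problems, and community of residence (among others"). That is six named items and an open end. Neither section gives a final covariate list, coding, centring, a selection rule, a limit on the number of terms, or error control for the interaction checks.

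The significance rule is general: "Parameter estimates with P-values less than .05 will be considered statistically significant". For post hoc work, "statistical tests will not be adjusted for multiple comparisons in post hoc analyses". The power paragraph in 17.1 covers only t-tests without covariates. Section 17.1 also calls significant findings preliminary and puts exploring trends ahead of significance.

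**The concern.** There are two separate problems.

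**Attendance.** Randomisation makes the groups comparable on everything fixed before allocation. Attendance accrues during the eight weeks, and the programme itself may change it. Holding it constant compares B-SWELL women with WE women who attended equally often, and randomisation does not protect that comparison. If B-SWELL improves outcomes partly by drawing women to more sessions, adjustment removes that part of the effect. If motivation drives both attendance and outcome, adjustment creates a motivation imbalance that was not there.

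**Interaction checks.** Fifty women give little information on moderation, and an open list judged at P<.05 easily yields a chance finding. Section 6.1 says the pilot's findings will be used to support a larger trial, so an adjusted effect estimate or an apparent moderator may be read with that trial in mind.

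**Working it through.** **Inputs from the documents.** 25 women per group ("N=50 total or N=25/group complete all four data collection time points with complete observations"); allocation "using 1:1 block randomization to promote equal group sizes"; "The statistical tests are two sided with a targeted significance level of 0.05"; a detectable effect of 0.87 SD at 85% power (17.1); four outcomes; six named demographics (6.3). The power text mentions four time points where the models use three; none of the t-test figures depends on this.

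**Assumptions not in the documents.** Number and coding of covariates; covariates independent of group; the size of any attendance difference and its relation to outcome.

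**1. The plan's own figure.** Standard error of a two-group difference in SD units: √(2/25) = 0.283. Noncentrality 0.87/0.283 = 3.08 on 48 df gives 85.4% power. The stated 85% reproduces.

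**2. Attendance.** Let δ be the difference in mean attendance between groups and γ the within-group slope of outcome on attendance, both in SD units. Then

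adjusted difference = unadjusted difference − γ × δ.

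| True difference | δ | γ | Adjusted difference |
|---|---|---|---|
| 0.50 | 0 | any | 0.50 |
| 0.50 | any | 0 | 0.50 |
| 0.50 | 0.5 | 0.20 | 0.50 − 0.10 = 0.40 |
| 0.50 | 0.5 | 0.42 | 0.50 − 0.21 = 0.29 |
| 0.50 | −0.5 | 0.42 | 0.50 + 0.21 = 0.71 |

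The 0.29 row matches a check in which attendance correlates 0.6 with motivation and motivation has a slope of 0.7 on the outcome (0.6 × 0.7 = 0.42).

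In the three-visit model with attendance as a time-constant covariate, the same shift of −0.21 applies at every visit. The baseline difference, truly 0, is reported as −0.21 and the week-8 difference as 0.29. The group-by-time contrast is 0.29 − (−0.21) = 0.50, unchanged. So the bias falls on the adjusted comparisons at each visit, not on differential change.

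**3. False moderators.** Six independent null tests at 0.05: 1 − 0.95^6 = 26.5%. Simulating 50 women with six interactions in one model gives about 25%. Over four outcomes, 24 independent tests: 1 − 0.95^24 = 70.8%. With outcomes correlated at an assumed 0.4, simulation gives about 63%.

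**4. Power for a true moderator.** An evenly split binary moderator makes four cells of 12.5 women. Standard error of the interaction: √(4/12.5) = 0.566, twice that of the group effect. For a true interaction of 0.87 SD, noncentrality is 0.87/0.566 = 1.54 on 46 df, and power is 32.5%. At 85% power the group contrast detects 0.865 SD, so the interaction would need about 2 × 0.865 = 1.73 SD.

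**5. Precision of the group effect.** Single visit, true effect 0.87 SD, covariates that explain no outcome variance:

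| Model | Median SE | Power |
|---|---|---|
| No covariates | 0.283 | 85% |
| Six binary, all interactions, centred | 0.302 | 79% |
| Six three-level, all interactions, centred | 0.344 | 67% |
| Six binary, all interactions, reference-coded | 0.856 | 17% |
| Six three-level, all interactions, reference-coded | 1.43 | 9% |

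The last two rows describe a woman in the reference category of every covariate, not the average effect. If covariates explain 20–30% of outcome variance, seven one-df covariates cost nothing (power 86–91%).

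In the three-visit model with complete data and an assumed within-person correlation of 0.5, the group-by-time standard error stays at 0.283 with or without covariate-by-group terms. It rises, to 0.334 (7 covariate df) or 0.469 (15 df), only if covariate-by-group-by-time terms are also fitted.

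**The case against.** The strongest reply is that this is a feasibility pilot that says its significant findings are preliminary and leaves efficacy to a later trial. That stands, and it limits the harm from a chance moderator. It does not lower the chance of finding one, and it does nothing about bias from attendance, which affects the estimate and not only its P-value.

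A second reply is that the text only checks interactions. It does not say that all are fitted together, kept, or present when the group effect is read, and the 6.3 table lists what is collected, not what enters the model. This is also fair. A reader might infer from the open-ended list that the precision of the group effect will collapse, to 17% or 9% power. The documents do not support that. Those figures need all interactions fitted together, uncentred coding, and the group effect read at the reference level at a single visit. Section 17.1 states none of these, although it rules none of them out. The powered t-tests contain no covariates, so their 85% is untouched.

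A third reply is that group-by-time, which measures differential change, is immune. With complete data and time-constant covariates that is correct. But 17.1 also plans comparisons of group means at each visit, and if these are taken from the adjusted model they carry the attendance bias.

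A reader might also infer that a false moderator would shape the design of the next trial. The documents say only that findings will support further research; no rule ties a moderator P-value to a design decision.

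**Conclusion.** The point holds for attendance and for the uncontrolled interaction checks. Adjusting for attendance can bias the model-adjusted 8- and 12-week comparisons by γ × δ: 0.21 SD in the illustration, in either direction, and zero if attendance is equal between groups or unrelated to outcome. The documents give neither quantity, so the size is an assumption; that attendance arises after randomisation is not.

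If six null interactions are tested, a false moderator appears about 25% of the time per outcome, and about 71% of the time over four outcomes if tests are independent. A true interaction of 0.87 SD would be found about one time in three. These figures assume six one-df checks, because the plan sets no number.

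Loss of precision in the group effect is a lesser matter: modest with centred terms and a short list, and severe only for an uncentred reference-level coefficient with every interaction in the model.

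**What to change.** Amend the Aim 2c text in section 17.1 as follows.

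- Remove attendance rate and its interaction with the intervention from the outcome models. Report attendance by group, descriptively, under Aim 2a.
- Take the intervention effect from a model with group, time and group-by-time, plus at most one or two baseline covariates named in advance, and no covariate-by-intervention terms.
- Keep baseline as a level of time in the response. Do not also enter the baseline outcome as a covariate, which would put the same measurement on both sides of the model.
- Present demographic moderators separately, as exploratory estimates with confidence intervals, and exempt them from the P<.05 rule.

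The cost is a change of wording, with no effect on data collection or sample size. The plan gives up significance tests of moderators, which have little power at this size.
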